1.6. Overview of Enzalutamide

Enzalutamide will be provided by Pfizer as capsules for oral administration. More detailed information about the known and expected benefits and risks and reasonably expected AEs of enzalutamide may be found in the Investigator's Brochure, which is the SRSD for this study.

2. STUDY OBJECTIVES AND ENDPOINTS

Part 1A - PF-06952229 Single Agent Dose Escalation Phase in Patients With Advanced/Metastatic Tumors.

Primary Objective(s):	Primary Endpoint(s):
 To assess safety and tolerability at increasing dose levels of PF-06952229 in patients with advanced/metastatic tumors. To determine MTD and RP2D of PF-06952229 as a single agent. 	 First-cycle DLTs. AEs as graded by NCI CTCAE version 5.0. Laboratory abnormalities as graded by NCI CTCAE version 5.0.
Secondary Objective(s):	Secondary Endpoint(s):
 To evaluate the single and multiple dose PK of PF-06952229 when given as a single agent. To evaluate preliminary anti-tumor activity of PF-06952229 when given as a single agent. To evaluate preliminary biochemical responses as a measure of anti-tumor activity of PF-06952229 	 Pharmacokinetic parameters of PF-06952229. Single Dose (SD) - C_{max}, T_{max}, AUC_{last}, and as data permit, AUC_{inf}, CL/F, V_z/F, and t_{1/2}. Multiple Dose (MD) - C_{ss,max}, T_{ss,max}, AUC_{last}, C_{ss,min}, and as data permit CL_{ss}/F, V_{ss}/F, t_{1/2}, and R_{ac} (AUC_{last}/AUC_{last}). PSA50 Response Rate for prostate cancer patients. Response assessment will be based on PCWG2 for prostate cancer and RECIST 1.1 for other tumor types.
CCI	

Part 1B - Dose Escalation of PF-06952229 in Combination With Enzalutamide in Patients with mCRPC

Primary Objective(s):	Primary Endpoint(s):
 To assess safety and tolerability at increasing dose levels of PF-06952229 in combination with enzalutamide in patients with mCRPC. To determine MTD and RP2D of PF-06952229 in combination with enzalutamide in patients with mCRPC. 	 First cycle DLTs in combination with enzalutamide for mCRPC. AEs as graded by NCI CTCAE version 5.0. Laboratory abnormalities as graded by NCI CTCAE version 5.0.
Secondary Objective(s):	Secondary Endpoint(s):
 To evaluate the single and multiple dose PK of PF-06952229 when given in combination with enzalutamide. To evaluate preliminary anti-tumor activity of PF-06952229 when given in combination with enzalutamide. To evaluate preliminary biochemical responses as a measure of anti-tumor activity of PF-06952229 when given in combination with enzalutamide. 	Pharmacokinetic parameters of PF-06952229. Single Dose (SD) - C _{max} , T _{max} , AUC _{last} , and as data permit, AUC _{inf} , CL/F, V _z /F, and t _{1/2} . Multiple Dose (MD) - C _{ss,max} , T _{ss,max} , AUC _{last} , C _{ss,min} , and as data permit CL _{ss} /F, V _{ss} /F, t _{1/2} , and R _{ac} (AUC _{last} /AUC _{last}). PSA50 Response Rate Response assessment will be based on PCWG2 and RECIST 1.1.

Part 2A - PF-06952229 Single Agent Dose Expansion Phase in mCRPC

Primary Objective(s):	Primary Endpoint(s):
 To confirm safety and tolerability of PF-06952229 at the estimated RP2D in patients with mCRPC. To estimate efficacy of PF-06952229 at the estimated RP2D in patients with mCRPC. To confirm the RP2D of PF-06952229 as a single agent. Secondary Objective(s): 	 AEs as graded by NCI CTCAE version 5.0. Laboratory abnormalities as graded by NCI CTCAE version 5.0. PSA50 Response Rate. Response assessment will be based on PCWG2 and RECIST 1.1. Secondary Endpoint(s):
To estimate additional efficacy of	ORR based on PCWG2 and RECIST 1.1. and
PF-06952229 at the estimated RP2D in patients with mCRPC.	time to event endpoints (DoR, PFS, OS, TTP, TTR).
To further evaluate the single and multiple dose	• Pharmacokinetic parameters of PF-06952229.
PK of PF-06952229 when given as a single agent.	 Single Dose (SD) - C_{max}, T_{max}, AUC_{last}, and as data permit, AUC_{inf}, CL/F, V_z/F, and t_{1/2}.
To evaluate immune cells in paired pre and post treatment tumor biopsies (where available).	 Multiple Dose (MD) - C_{ss,max}, T_{ss,max}, AUC_{last}, C_{ss,min}, and as data permit CL_{ss}/F, V_{ss}/F, t_{1/2}, and R_{ac} (AUC_{last}/AUC_{last}). Assessment of levels of intra-tumor T cells (eg,
	CD8 IHC);
CCI	

Part 2B - Dose Expansion of PF-06952229 in Combination With Enzalutamide in Patients With mCRPC

Primary Objective(s):	Primary Endpoint(s):
 To confirm PF-06952229 safety profile in combination with enzalutamide at the estimated RP2D in patients with mCRPC. To estimate efficacy of PF-06952229 in combination with enzalutamide at the estimated RP2D in patients with mCRPC. To confirm the RP2D of PF-06952229 in combination with enzalutamide in patients with mCRPC. 	 AEs as graded by NCI CTCAE version 5.0. Laboratory abnormalities as graded by NCI CTCAE version 5.0. PSA50 Response Rate. Response assessment will be based on PCWG2 and RECIST 1.1.
Secondary Objective(s):	Secondary Endpoint(s):
 To estimate additional efficacy of PF-06952229 at the estimated RP2D in patients with mCRPC. To further evaluate the PK of PF-06952229 when given in combination with enzalutamide. To evaluate immune cells in paired pre and post treatment tumor biopsies (where available). 	 ORR based on PCWG2 and RECIST 1.1. and time to event endpoints (DoR, PFS, OS, TTP, TTR). Pharmacokinetic parameters of PF-06952229 (in at least 8 subjects). Single Dose (SD) - C_{max}, T_{max}, AUC_{last}, and as data permit, AUC_{inf}, CL/F, V_z/F, and t_{1/2}. Multiple Dose (MD) - C_{ss,max}, T_{ss,max}, AUC_{last}, C_{ss,min}, and as data permit CL_{ss}/F, V_{ss}/F, t_{1/2}, and R_{ac} (AUC_{last}/AUC_{last}). Peak and trough concentrations at selected cycles. Assessment of levels of intra-tumor T cells (eg, CD8 IHC);

3. STUDY DESIGN

3.1. Study Overview

This is a Phase 1, open-label, multi-center, multiple-dose, dose-escalation and expansion, safety, tolerability, PK, and PD study of PF-06952229 in previously treated patients with advanced or metastatic cancers that may have high TGFβ signatures and EMT expression.

The study includes Parts 1A and 1B, which are dose-escalation cohorts, and Parts 2A and 2B, which are dose expansion cohorts. The primary objectives for Part 1A are to assess the safety and tolerability of PF-06952229 administered as a single agent and to determine maximum tolerated dose (MTD). The primary objectives for Part 1B are to assess the safety and tolerability of PF-06952229 administered with enzalutamide and to determine MTD. The primary objectives for Part 2A are to confirm PF-06952229 safety and tolerability, estimate the single agent efficacy of PF-06952229 and determine a recommended Phase 2 dose (RP2D). The primary objectives of Part 2B are to confirm the safety profile of PF-06952229 combined with enzalutamide, estimate the efficacy of PF-06952229 combined with enzalutamide and determine a RP2D for the combination.

Part 1A is a sequential single-agent dose-escalation conducted in patients with advanced or metastatic solid tumors who have failed standard-of-care treatment or for whom no standard-of-care exists. Successive cohorts of patients are to receive escalating doses of PF-06952229 on an outpatient basis starting from 20 mg BID, which is based on non-clinical data. Nine candidate dose levels are planned using an Accelerated Titration Design (ATD) until reaching 250 mg BID, after which the design will revert to modified target probability interval (mTPI). The highest tested dose will not exceed 800 mg BID. If an MTD is not observed during the 28-day safety window, additional dose levels may be considered based on PK, safety, tolerability, CCI assessments. Based on PK and safety, additional patients can be added to a dose lower than the MTD and also may be moved forward to monotherapy expansion.

Part 1B is a dose-escalation of PF-06952229 in the combination with enzalutamide conducted in patients who were previously treated for metastatic castration-resistant prostate cancer (mCRPC). The starting dose of PF-06952229 will be based on safety, PK, and potential efficacy, but will not exceed the MTD or MAD of Part 1A. Because of the potential DDI between enzalutamide and PF-06952229, the maximum PF-06952229 dose for the combination may be higher than the monotherapy MTD, but not higher than 800 mg BID.. Based on evolving PK, PD, and safety profiles, assessed in Part 1A, Part 1B may commence before reaching the MTD in Part 1A, and will follow an mTPI design. The maximum PF-06952229 dose for the combination escalation may be higher than the monotherapy MTD due to the potential DDI between enzalutamide and PF-06952229, but not higher than 800 mg BID.

Part 2A and Part 2B are expansion cohorts for monotherapy and combination therapy, respectively, in patients with previously treated mCRPC.

To assess baseline $TGF\beta$ related biomarker signatures that may correlate with clinical efficacy, all patients enrolled in Part 1 will be required to provide a recent archival tumor

sample or to undergo a fresh pre-treatment biopsy if archival samples are unavailable prior to trial treatment.

Part 2 patients are required to provide either a recent archival tumor biopsy or, for all patients in Part 2A and from approximately 10 patients in Part 2B, mandatory de novo biopsies. Mandatory de novo pre-treatment and on-treatment tumor biopsies may not be required where it is determined that it is not medically feasible (such as constituting unacceptable medical risks). However, this would require agreement of Investigator and Sponsor.

The biomarker studies will be used to help understand the in vivo mechanism of action of the agent(s) studied as well as potential mechanisms of resistance. The studies may help in the future development of PF-06952229 as a single agent, or in combination with other compounds, and may provide information on tumor sub-types that may respond to the Investigational Product.

[figure not shown]
Approximately 90 patients are to be enrolled in this study. The total sample size may vary depending on the number of the dose levels with patients enrolled and the actual number of patients at each dose level. A maximum sample size of 40 patients may be needed to establish and confirm MTD in Part 1A, and approximately 20 patients may be needed for Part 1B. A maximum of 10 and 20 patients are planned for the expansion cohorts in Part 2A and Part 2B, respectively.

All patients:

- 1. Will undergo up to 4 weeks of screening prior to study entry ie, Cycle 1 Day 1.
- 2. Will receive doses of PF-06952229, administered orally on 28-day cycle, 7 days on, 7 days off, for up to 2 years. Any additional treatment with PF-06952229 beyond 2 years shall be discussed and approved by the Sponsor.
- 3. Treatment with investigational product (IP) will continue until disease progression, patient refusal, or unacceptable toxicity occurs, whichever occurs first. However, patients who demonstrate clinical benefit (despite radiographic progression) with manageable toxicity and are willing to continue receiving the investigational product will be given the opportunity to continue treatment upon agreement between investigator and sponsor.
- 4. Will undergo a follow-up visit approximately 4 weeks after the last dose for AE and serious adverse event (SAE) collection.

The proposed doses, schedule(s), and PK and PD time points may be reconsidered and amended during the study based on the emerging safety and PK and PD data.

Figure 2. Study Schema

3.1.1. Part 1 Dose Escalation

3.1.1.1. Part 1A - Single Agent PF-06952229 in Advanced/Metastatic Solid Tumors

Part 1A is a sequential single-agent dose-escalation conducted in patients with advanced or metastatic solid tumors who have failed standard-of-care treatment or for whom no standard-of-care exists.

3.1.1.2. Starting Dose

The starting dose of PF-06952229 will be 20 mg given twice daily (BID) orally as a regimen of 7 days on/7 days off in 28- day cycles. The rationale for selecting this starting dose is provided in Section 1.3.

3.1.1.3. Criteria for Dose Escalation

The initial dose escalation in Part 1A begins with an accelerated titration design followed by a standard escalation phase that will use a modified target probability interval (mTPI) approach. Initial dose levels for Part 1A are provided in Table 1 and intermediate dose levels may be considered if needed.

Table 1.	PF-0	6952229	Dose]	Levels
Table 1.	1 1 - 1	ひきらんとんご	DUSC 1	

DOSE LEVEL (DL)*	DOSE	Percent Increase From Previous Dose
DL -1	10 mg BID	-
DL 1** Starting dose	20 mg BID	-
DL 2	40 mg BID	100%
DL 3	80 mg BID	100%
DL 4	150 mg BID	88%
DL 5	250 mg BID	66%
DL 6	375 mg BID	50%
DL 7	500 mg BID	33%
DL 8	625 mg BID	25%
DL 9	750 mg BID	16.7%

^{*}The proposed doses, schedule(s), and PK time points may be reconsidered or amended during the study based on the emerging safety and PK data. Intermediate doses may be considered when deemed necessary based on on-going evaluation of safety and toxicity data.

In principle, all patients must be evaluated for a minimum DLT observation period of 28 days. However, if a patient discontinues close to Day 28 for reasons other than toxicity and due to an evident non drug-related event, the patient may be deemed evaluable for safety if safety assessments have been unremarkable and the investigator and sponsor's medical monitor both agree that the patient is evaluable for DLT safety observation.

The dose escalation in the study will stop if any of the following criteria is met:

- Approximately 40 patients have been achieved in Part 1A monotherapy dose escalation, or approximately 20 patients have been achieved in Part 1B combination dose escalation;
- 6 12 patients have been enrolled at a dose level that is predicted to be the MTD per the mTPI method:
- All dose levels explored appear to be overly toxic, and the MTD cannot be determined.

3.1.1.3.1. Acceleration Phase

The dose escalation in Part 1A – Monotherapy Dose Escalation will use the Accelerated Titration Design (ATD) as proposed by Simon⁷ followed by a standard escalation phase that will use a mTPI approach. During the accelerated phase, initial cohorts will contain a minimum of 1 patient until the first instance of first-course CTCAE clinically significant grade ≥ 2 toxicity (as agreed upon by investigator and sponsor). With the occurrence of clinically significant grade ≥ 2 toxicity, a minimum of 2 additional patients will be treated at

^{**}Starting dose DL1. De-escalation to a lower dose level (DL-1) may be considered if DLT(s) at the starting dose are observed (see Table 2 on mTPI Dose Decision Rules).

that dose. If these 2 patients do not develop CTCAE grade ≥2 toxicity then the accelerated phase of the study with a minimum of 1 patient cohort will be continued. The dose escalations in this phase are in increments of approximately 80 - 100%, until reaching 250 mg BID, after which the design will revert to a standard escalation approach (mTPI) in order to obtain more comprehensive PK data. The accelerated phase will revert to standard escalation (see below for underlying methodology) if there is a second occurrence of first-course cycle CTCAE grade ≥2 or first instance of first-course cycle DLT.

3.1.1.4. Standard (mTPI) Escalation Phase

The proposed mTPI method for this protocol includes stopping rules and dose escalation/finding criteria which prevent the target DLT rate to reach ≥33% for determining the MTD. Targeting a DLT rate of 27.5% and an acceptable DLT interval (22.5% to 32.5%) will be utilized in both Parts 1A – Monotherapy Dose Escalation (beginning at Dose Level 5) and 1B – Combination Dose Escalation, and will also be used to monitor the DLTs so as not to cross toxicity boundaries in the expansion of a cohort. At least 3 DLT-evaluable patients will be required for the dose escalation decision based on mTPI beginning at Dose Level 5. Note provided the DLT rate for cardiac toxicity does not exceed 10%. The decision rules use a Beta (1,1) prior.

Table 2. mTPI Dose Decision Rules

DLT	n=1	n=2	n=3	n=4	n=5	n=6	n=7	n=8	n=9	n=10	n=11	n=12
0	Е	Е	Е	Е	Е	Е	Е	Е	Е	Е	Е	Е
1	D	S	S	S	S	S	Е	Е	Е	E	Е	Е
2		DU	D	D	S	S	S	S	S	S	S	Е
3			DU	DU	D	D	S	S	S	S	S	S
4				DU	DU	DU	DU	D	S	S	S	S
5					DU	DU	DU	DU	DU	D	S	S
6						DU	DU	DU	DU	DU	DU	DU
7							DU	DU	DU	DU	DU	DU
8								DU	DU	DU	DU	DU
9									DU	DU	DU	DU
10										DU	DU	DU
11											DU	DU
12												DU

Source: https://udesign.laiyaconsulting.com/

E: Escalate to the next higher dose; S: Stay at the same dose; D: De-escalate to the previous lower dose; DU: De-escalate to the previous lower dose and the current dose will never be used again in the trial.

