3.3. MTD Definition

A DLT rate of 27.5% with an equivalence interval of (22.5%, 32.5%) (note: provided the DLT rate for cardiac toxicity does not exceed 10%) will be utilized to estimate the MTD; patients will be enrolled in dose cohorts of 2-4 patients, and each patient will receive 2 courses of PF-06952229 (7 days on, 7 days off) in a 28 day cycle. Due to the discreteness of the dose levels and in the interest of the safety of patients, the estimated MTD is the highest tested dose level with DLT rate ≤ approximately 32.5%. The dose finding decision will be based on a 1-cycle (28 day) DLT observation period.

At least 6 patients have been accumulated on a dose that can be predicted to be the MTD.

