Due to binomial data variability in small samples, DLTs may be observed in a first cohort(s) by chance even when the true Probability (DLT) is fairly low. This could result in the estimated posterior DLT rate to exceed the targeted 27.5% very early in the trial.

The following table shows the probability of escalating to the next dose level for a range of underlying true DLT rates. For example, for a DLT that occurs in 10% of patients, there is a greater than 90% probability of escalating. Conversely, for a DLT that occurs with a rate of 70%, the probability of escalating is 3%. It is assumed that dose escalation occurs with either 0/3 or 1/6 patients with DLTs.

Probability of Escalating Dose

True underlying DLT rate	10%	20%	30%	40%	50%	60%	70%	80%	90%
Probability of escalating dose	0.91	0.71	0.49	0.31	0.17	0.08	0.03	0.009	0.001

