9.6. Sample Size Determination

9.6.1. Part 1

In Part 1, patients will participate in a dose escalation phase aimed at estimating the MTD. The sample size for this component of the study will vary depending on the number of DLTs observed.

A maximum of 60 patients are expected to be enrolled in the dose escalation safety cohorts in Part 1, including approximately 40 patients for the monotherapy dose escalation and approximately 20 patients for the combination dose escalation. The actual number of patients enrolled will depend on the tolerability of PF-06952229 and the number of dose levels required to identify the MTD/RP2D. It is expected that the dose escalation process can be stopped and MTD declared with approximately 6 to 12 patients at the MTD dose. As for the number of patients treated at each dose, it is expected to be at 1 to 4 patients for the doses actually studied. However, since variable cohort size is allowed, the actual number of patients treated at each dose (including MTD) will vary from 1 to 12 patients.

9.6.2. Part 2

For PF-06952229 single agent expansion in patients with mCRPC, the planned sample size of the expansion cohort is 10 based on clinical consideration.

PF-06952229 single agent in combination with enzalutamide for patients with metastatic castration-resistant prostate cancer (mCRPC), assuming a sample size of 20, and the observed PSA50 response is 60% (12/20), the Bayesian posterior probability to demonstrate that the "True PSA50 response" is greater than 37% is 98.15%. Assuming 80% of the 20 patients have measurable disease and are response evaluable (16 patients evaluable), and the observed ORR is 43.75% (7/16), the Bayesian posterior probability to demonstrate that the "True ORR" is greater than 30% is 86.89%.

All the Bayesian calculations above assume a non-informative Uniform (0,1) prior

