Appendix 2. Detailed Dose Escalation/De-Escalation Scheme for mTPI design

DLT	n=1	n=2	n=3	n=4	n=5	n=6	n=7	n=8	n=9	n=10	n=11	n=12
0	E	E	E	E	E	E	E	E	E	E	E	E
1	D	S	S	S	S	S	Е	Е	Е	Е	Е	E
2		DU	D	D	S	S	S	S	S	S	S	E
3			DU	DU	D	D	S	S	S	S	S	S
4				DU	DU	DU	DU	D	S	S	S	S
5					DU	DU	DU	DU	DU	D	S	S
6						DU	DU	DU	DU	DU	DU	DU
7							DU	DU	DU	DU	DU	DU
8								DU	DU	DU	DU	DU
9									DU	DU	DU	DU
10										DU	DU	DU
11											DU	DU
12												DU

Source: https://udesign.laiyaconsulting.com/.

E: Escalate to the next higher dose; S: Stay at the same dose; D: De-escalate to the previous lower dose; DU: De-escalate to the previous lower dose and the current dose will never be used again in the trial.

Escalation/De-escalation algorithms for total number of patients treated at the current dose level (current and previous cohorts)

- With 2 patients treated at current dose level:
 - 0 DLT -> escalate;
 - 1 DLT -> remain at the same dose;
 - 2 DLTs -> de-escalate and consider current dose as intolerable.
- With 3 patients treated at current dose level:
 - 0 DLT -> escalate;
 - 1 DLT -> remain at the same dose;
 - 2 DLTs -> de-escalate;
 - 3 DLTs -> de-escalate and consider current dose as intolerable.
- With 4 patients treated at current dose level:
 - 0 DLT -> escalate;
 - 1 DLT -> remain at the same dose;

- 2 DLT -> de-escalate;
- 3-4 DLTs -> de-escalate and consider current dose as intolerable.
- With 5 patients treated at current dose level:
 - 0 DLT -> escalate;
 - 1-2 DLTs -> remain at the same dose;
 - 3 DLTs -> de-escalate;
 - 4-5 DLTs -> de-escalate and consider current dose as intolerable.
- With 6 patients treated at current dose level:
 - 0 DLT -> escalate;
 - 1-2 DLT -> remain at the same dose;
 - 3 DLTs -> de-escalate;
 - 4-6 DLTs -> de-escalate and consider current dose as intolerable.
- With 7 patients treated at current dose level:
 - 0-1 DLT -> escalate;
 - 2-3 DLTs -> remain at the same dose;
 - 4-7 DLTs -> de-escalate and consider current dose as intolerable.
- With 8 patients treated at current dose level:
 - 0-1 DLT -> escalate;
 - 2-3 DLTs -> remain at the same dose;
 - 4 DLTs -> de-escalate;
 - 5-8 DLTs -> de-escalate and consider current dose as intolerable.
- With 9 patients treated at current dose level:
 - 0-1 DLT -> escalate;
 - 2-4 DLTs -> remain at the same dose;

- 5-9 DLTs -> de-escalate and consider current dose as intolerable.
- With 10 patients treated at current dose level:
 - 0-1 DLT -> escalate;

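### From Dose Level 5 the protocol requires three DLT-evaluable patients before an mTPI escalation decision, yet Appendix 2 escalates on no DLT in two treated patients

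*Protocol*

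**What the plan says.** Protocol Section 3.1.1.4, which introduces the mTPI phase, sets a floor: "At least 3 DLT-evaluable patients will be required for the dose escalation decision based on mTPI beginning at Dose Level 5". Table 2 stands directly below it. Its key reads "E: Escalate to the next higher dose; S: Stay at the same dose", and its zero-DLT row shows E in every column, including n=1 and n=2.

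Appendix 2 reprints the grid and then spells it out in words. Under the item "With 2 patients treated at current dose level" the first line is "0 DLT -> escalate". Nothing there mentions a minimum of three or a dose level. The word list starts at two patients, so escalation on 0 of 1 appears only in the two grids. Its counts are cumulative over all cohorts at the dose, and they are counts of patients treated. Section 3.2 defines DLT-evaluable more narrowly: a DLT, or at least 75% of planned doses of each investigational product together with all scheduled safety assessments.

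On cohort size, Section 3.3 says "patients will be enrolled in dose cohorts of 2-4 patients", and SAP 9.1 says the same. On patients per dose, Section 9.6.1 says "it is expected to be at 1 to 4 patients for the doses actually studied". SAP 5.2.1 and 5.2.2, which hold the SAP's escalation and MTD rules, do not carry the minimum of three.

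Section 9.2.2 and SAP 5.2.2 publish a table of escalation probabilities with this premise: "It is assumed that dose escalation occurs with either 0/3 or 1/6 patients with DLTs". Part 1B is sent to Section 3.1.1.4 for its design (Section 3.1.1.5).

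**The concern.** From Dose Level 5, a completed cohort of two with no DLT is an instruction to escalate under Appendix 2, but not yet a basis for a decision under Section 3.1.1.4. No passage says which prevails. Because a cohort of two is a planned size, 0 of 2 is a point the trial can actually reach.

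Three things add to the ambiguity. The SAP's decision sections omit the floor, so a reader working from the SAP would not find it there. Appendix 2 counts treated patients, so two treated could mean fewer than two evaluable. And it is unclear whether the words about Dose Level 5 limit the floor in Part 1B, which borrows the same section.

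At stake is how readily the trial moves up from a dose whose true DLT rate lies above the target interval of 22.5% to 32.5%.

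**Working it through.** **Inputs.** Table 2 and Appendix 2 grids; floor of three (3.1.1.4); cohorts of 2 to 4 (3.3, SAP 9.1); published escalation table (9.2.2, SAP 5.2.2). Write p for the true DLT rate and q = 1 − p. All treated patients are taken as evaluable and independent.

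**1. The published table reproduces.** Escalating on 0/3, or on 1/3 followed by 0/3, has probability q³ + 3pq²·q³:
- p = 0.3: 0.343 + 0.441 × 0.343 = 0.494 (published 0.49)
- p = 0.4: 0.216 + 0.432 × 0.216 = 0.309 (0.31)
- p = 0.5: 0.125 + 0.375 × 0.125 = 0.172 (0.17)
- p = 0.6: 0.064 + 0.288 × 0.064 = 0.082 (0.08)

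The other five entries match as well.

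**2. The E entries at n=1 and n=2 are genuine.** Recomputing the unit probability masses on (0, 0.225), (0.225, 0.325) and (0.325, 1), with DU where the posterior probability of a rate above 0.275 exceeds 0.95, gives all 90 cells of Table 2 under the Beta(1,1) prior of 3.1.1.4. Under the Beta(0.5,0.5) prior of 9.2.2 four cells change (1/5, 1/6, 2/4, 2/11), but 0/1 and 0/2 remain E.

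**3. First look on two patients.** The chance of 0/2 is q²: 0.49, 0.36, 0.25, 0.16.

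**4. Whole path through Table 2, cohorts of two, at most 12 patients at the dose, ending at the first E, D or DU.** The relevant cells are: 1/2 to 1/6 S; 1/7 and beyond E; 2/2 DU; 2/4 D; 2/6 to 2/10 S; 2/12 E. With three or more DLTs, E is never reached by n=12.
- Without the floor: q² + 2pq³·q⁴·(1 + 4pq³). At p = 0.4: 0.36 + 0.0224 × 1.3456 = 0.390.
- With a floor of three (so that the first permitted E is at n=4): q⁴·(1 + a + a²), where a = 4pq³. At p = 0.4, a = 0.3456: 0.1296 × 1.465 = 0.190.

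| True DLT rate | Published (0/3 or 1/6) | First look 0/2 | Path, cohorts of 2, no floor | Path, cohorts of 2, floor of 3 |
|---|---|---|---|---|
| 30% | 0.49 | 0.49 | 0.56 | 0.38 |
| 40% | 0.31 | 0.36 | 0.39 | 0.19 |
| 50% | 0.17 | 0.25 | 0.26 | 0.08 |
| 60% | 0.08 | 0.16 | 0.16 | 0.03 |

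**5. Sensitivity.** The last column adds whole cohorts of two, so a decision waits for four patients. Cohorts of three, where the first look is at exactly three, give 0.44, 0.25, 0.14 and 0.07. These lie between the two paths.

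**6. Limit of the comparison.** The published table escalates at 1/6, where Table 2 says S. It is therefore not the Table 2 rule under either reading.

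**The case against.** The best answer is that the floor simply restricts a generic grid. It sits in the same section as Table 2, the grid is software output filled in for every n from 1 to 12, and a specific condition normally governs a generic table. For Table 2 this is a fair reading. It does not dispose of Appendix 2, which gives the two-patient instruction in words, elsewhere in the document, without a condition.

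The n=1 and n=2 columns also have a use. The floor starts at Dose Level 5, and below that level the acceleration phase allows one-patient cohorts and can revert to mTPI after a DLT or a second grade 2 or higher event (Section 3.1.1.3.1). That is right, so E at 0/1 and 0/2 is no contradiction at the lower levels. But neither grid says that those columns stop there.

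Several stronger inferences should be resisted:
- **That cohorts of two contradict a minimum of three.** Counts accumulate across cohorts, so a cohort of two can be supplemented before a decision.
- **That sites could escalate by themselves.** Under Section 5.1 the sponsor allocates the dose level and must give written permission to dose.
- **That 0/2 against 0/3 alone (for example 0.49 against 0.34 at 30%) is the excess over the published table.** That table also counts 1/6, and at 30% the first-look excess is nil.
- **That escalation on two patients has happened.** Appendix 10 reports six patients at 250 mg BID and three at 375 mg BID before the partial hold, which is compatible with the floor.

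The treated-versus-evaluable difference is softened by the definition of evaluability and the replacement provision in Section 3.2, but Appendix 2 does not refer to them.

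**Conclusion.** The inconsistency stands, and it is narrow: from Dose Level 5, Section 3.1.1.4 and Appendix 2 give different instructions at 0 DLTs in 2 patients. The unrestricted E entries, the SAP's silence, the treated-patient count and the open question for Part 1B leave it unresolved.

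If the two-patient instruction is followed, the first-look chance of escalating exceeds the published table by about 0, 5, 8 and 8 percentage points at true DLT rates of 30%, 40%, 50% and 60%. In cohorts of two, the choice of reading changes the whole-path chance from 0.39 to 0.19 at 40%, and about threefold at 50% (0.26 against 0.08). These figures assume that every treated patient is evaluable, whole cohorts of two and a cap of 12 per dose. Topping up to exactly three would narrow the gap.

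This is two written rules in conflict, curable by editing. It does not show that the mTPI grid is miscalculated or that any patient was escalated improperly.

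**What to change.** Reconcile Sections 3.1.1.4 and Table 2, Appendix 2, and SAP 5.2.1–5.2.2 as follows:
- State one minimum number of DLT-evaluable patients for an escalation decision, in both documents. Which number applies is for the sponsor to decide.
- Say which dose levels it covers, and whether and how it applies in Part 1B.
- Footnote only the E entries at n=1 and n=2 in both grids, and qualify the two-patient line in the Appendix 2 list. Leave the D, S and DU entries as they are, since the floor concerns escalation only.
- Replace counts of treated patients in Appendix 2 with counts of DLT-evaluable patients.
- Make the premise of the escalation-probability table in 9.2.2 and SAP 5.2.2 match the reconciled rule, and recompute the table if the premise changes.

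The cost is an edit to two tables and a few sentences. If a minimum above two is kept, a two-patient cohort without a DLT needs at most one or a few more patients before a decision, which slows escalation slightly at tolerable doses too: at a true rate of 10%, the whole-path chance in cohorts of two is 0.90 with the floor of three and 0.93 without it.
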